	
constant $[K_{el}]$, mean residence time [MRT] and time to maximum concentration $[T_{max}]$) will be determined and presented graphically and descriptively (as appropriate).
 
A detailed SAP will be finalized prior to final database lock. Any significant changes to the analyses described in this protocol will be highlighted in the SAP and the Clinical Study Report.

Duration of the Study	The planned duration of the entire study is approximately 30 months with an enrolment period of 12 months.
End of Study	The study will be completed 36 weeks after the last patient receiving 1 st treatment with SCB01A

Table 1: Study Schedule, Run-in phase (Dose 1, 0a, 1a, 2, 2a, 3, 3a, and 4 SCB01A)

Study Visit ¹	Screening	C1D1	C1D8	C1D15	C2D1	C2D8	C2D15	C3D1	C3D8	C3D15	C4D1-CXD1 ⁴	C4D8-CXD8 ⁴	EOT/Early Withdrawal ²	Follow-Up (Phone Call) ³	Un-scheduled
Study Days	-28 to -1	1 (± 0)	8 (± 1)	15 (± 2)	22 (± 1)	29 (± 1)	36 (± 2)	43 (± 1)	50 (± 1)	57 (± 2)	64 (± 1)	71 (± 1)	NA	NA	NA
Activities															
Informed Consent	X														
Medical History	X														
Eligibility Criteria	X	X													
Physical Examination	X	X	X	X	X	X	X	X	X	X	X	X			X
Vital Signs	X	X	X	X	X	X	X	X	X	X	X	X			X
BSA Calculation		X	X		X	X		X	X		X	X			
ECOG Performance Status	X	X	X	X	X	X	X	X	X	X	X	X			X
Adverse Events Review ⁵	X	X	X	X	X	X	X	X	X	X	X	X		X	X
Concomitant Medication Review	X	X	X	X	X	X	X	X	X	X	X	X		X	X
12-Lead ECG ⁶	X	X	X		X	X		X	X		X	X			X ¹⁶
Radiological Image Assessments ⁷	X										X			X	X ¹⁶
Safety Laboratory	X	X ⁸	X	X	X	X	X	X	X	X	X	X			X ¹⁶
Urinalysis	X	X ⁸			X			X			X			X	X ¹⁶
Serum Pregnancy Test ⁹	X														
Coagulation		X ⁸	X	X	X	X	X	X	X	X	X	X			X ¹⁶
HPV	X														
Study Drug Administration		X	X		X	X		X	X		X	X			
EORTC Questionnaires ¹⁰	X		X	X	X	X	X	X	X	X	X	X			
PK ¹¹		X	X		X	X		X	X						
Biomarker ¹²		X								X					

Study Visit ¹	Screening	C1D1	C1D8	C1D15	C2D1	C2D8	C2D15	C3D1	C3D8	C3D15	C4D1-CXD1 ⁴	C4D8-CXD8 ⁴	EOT/Early Withdrawal ²	Follow-Up (Phone Call) ³	Un-scheduled
Study Days	- 28 to -1	1 (± 0)	8 (± 1)	15 (± 2)	22 (± 1)	29 (± 1)	36 (± 2)	43 (± 1)	50 (± 1)	57 (± 2)	64 (± 1)	71 (± 1)	NA	NA	NA
Activities															
DCE-MRI ¹³	X	X													
Survival Status ¹⁴														X	
Cancer Therapy ¹⁵														X	
Nerve Conduction Velocity ¹⁷	X														

¹ Patients may continue treatment beyond 3 cycles (9 weeks) of SCB01A treatment per investigator discretion if they are experiencing clinical benefit, until the study is terminated.

² EOT visit should be conducted 21 \pm 2 days after the last infusion. Early withdrawal visit should be conducted within 21 days after the patient received the last dose of study treatment.

³ Follow-up visits will be performed after the patient completes EOT visit or early withdrawal visit. Follow-up visits will be scheduled every 3 weeks for 9 weeks, thereafter every 9 weeks until the end of the study. These visits can be conducted by phone.

⁴ Starting from cycle 4, there will be no study visit on Day 15.

⁵ All AEs including SAEs must be reported from the time of informed consent signed and must continue to be followed for 28 days after last administration of study treatment.

⁶ ECG will be performed prior to study drug administration, within 1 hour following study drug administration, 2 hours after study drug administration, immediately after the 3 hour infusion, 4 hours after study drug administration, and 24 hours after administration of the study drug. Starting from Cycle 4, the ECG will be obtained at every treatment cycle within 1 hour following study drug administration and at EOT/early withdrawal visit (time window: ± 5 min).

⁷ Tumor assessments should be performed at baseline, and every 3 cycles prior to next cycle until progression of disease. For patients who meet DC criteria after the first 3 cycles of study treatment, additional radiological tumor assessments should be performed at Week 12. Any additional assessment can be arranged when clinically indicated.

⁸ Test results within 7 days prior to Cycle 1, Day 1 (C1D1) are acceptable. Only items not performed or obtained within 7 days prior to C1D1 should be tested.

⁹ Serum pregnancy test for women of childbearing potential must be performed \leq 14 day prior to first dose.

¹⁰ Quality of Life questionnaires (EORTC QLQ-C30 and H&N35) should be performed at Screening and all clinic visits (before study drug administered, where applicable, except at C1D1).

¹¹ PK blood samples will be taken immediately pre-infusion then at 2, 3, 4, 6, 10, 21 and 24 hours after start of infusion on Day 1 and Day 8 of Cycles 1, 2 and 3 (time window: ± 5 min).

¹² Blood Sample for VEGF and CEC will be taken immediately pre-infusion then at 6, 10 and 24 hours after start of infusion on C1D1 and C3D15. Blood Samples for CEP will be taken immediately pre-infusion and C3D15.

¹³ Tumor microvessel density and blood flow by DCE-MRI at both baseline (-28 to -1 Day) and 6 hours (+/- 1hour) after the infusion of the drug on C1D1.

¹⁴ Follow-up for survival status will be performed via telephone call if the site is unable to confirm via chart review or clinical visit.

¹⁵ Cancer therapies evaluated at the Follow-Up visit or phone call include anti-cancer medications, cancer-related radiotherapy and cancer-related surgery/procedures since last contact.

¹⁶ To be performed when necessary at the patient's request or per Investigator decision.

¹⁷ To be performed for all patients at baseline and then during the trial only if grade 2 or above neurological symptoms experienced by the patient after receiving treatment with SCB01A. Refer section 5.9 for further details.

Table 2: Study Schedule, Phase II, Stage 1 and Stage 2, Optimal dose SCB01A

Study Visit ¹	Screening	C1D1	C1D8	C1D15	C2D1	C2D8	C2D15	C3D1	C3D8	C3D15	C4D1-CXD1 ⁴	C4D8-CXD8 ⁴	EOT/Early Withdrawal ²	Follow-Up (Phone Call) ³	Un-scheduled
Study Days	-28 to -1	1 (±0)	8 (±1)	15 (±2)	22 (±1)	29 (±1)	36 (±2)	43 (±1)	50 (±1)	57 (±2)	64 (±1)	71 (±1)	NA	NA	NA
Activities															
Informed Consent	X														
Medical History	X														
Eligibility Criteria	X	X													
Physical Examination	X	X	X	X	X	X	X	X	X	X	X	X			X
Vital Signs	X	X	X	X	X	X	X	X	X	X	X	X			X
BSA Calculation		X	X		X	X		X	X		X	X			
ECOG Performance Status	X	X	X	X	X	X	X	X	X	X	X	X			X
Adverse Events Review ⁵	X	X	X	X	X	X	X	X	X	X	X	X		X	X
Concomitant Medication Review	X	X	X	X	X	X	X	X	X	X	X	X		X	X
12-Lead ECG ⁶	X	X	X		X	X		X	X		X	X			X ¹⁵
Radiological Image Assessments ⁷	X										X			X	X ¹⁵
Safety Laboratory	X	X ⁸	X	X	X	X	X	X	X	X	X	X			X ¹⁵
Urinalysis	X	X ⁸			X			X			X			X	X ¹⁵
Serum Pregnancy Test ⁹	X														
Coagulation		X ⁸	X	X	X	X	X	X	X	X	X	X			X ¹⁵
HPV	X														
Study Drug Administration		X	X		X	X		X	X		X	X			
EORTC Questionnaires ¹⁰	X		X	X	X	X	X	X	X	X	X	X			
Biomarker ¹¹		X								X					
DCE-MRI ¹²	X	X													

Study Visit ¹	Screening	C1D1	C1D8	C1D15	C2D1	C2D8	C2D15	C3D1	C3D8	C3D15	C4D1-CXD1 ⁴	C4D8-CXD8 ⁴	EOT/Early Withdrawal ²	Follow-Up (Phone Call) ³	Un-scheduled
Study Days	- 28 to -1	1 (± 0)	8 (± 1)	15 (± 2)	22 (± 1)	29 (± 1)	36 (± 2)	43 (± 1)	50 (± 1)	57 (± 2)	64 (± 1)	71 (± 1)	NA	NA	NA
Activities															
Survival Status ¹³														X	
Cancer Therapy ¹⁴														X	
Nerve Conduction Velocity ¹⁶	X ¹⁶														

¹ Patients may continue treatment beyond 3 cycles (9 weeks) of SCB01A treatment per investigator discretion if they are experiencing clinical benefit, until the study is terminated.

² EOT visit should be conducted 21 \pm 2 days after the last infusion. Early withdrawal visit should be conducted within 21 days after the patient received the last dose of study treatment.

³ Follow-up visits will be performed after the patient completes EOT visit or early withdrawal visit. Follow-up visits will be scheduled every 3 weeks for 9 weeks, thereafter every 9 weeks until the end of the study. These visits can be conducted by phone.

⁴ Starting from cycle 4, there will be no study visit on Day 15.

⁵ All AEs including SAEs must be reported from the time of informed consent signed and must continue to be followed for 28 days after last administration of study treatment.

⁶ ECG will be performed prior to study drug administration, within 1 hour following study drug administration, 2 hours after study drug administration, immediately after the 3 hour infusion, 4 hours after study drug administration, and 24 hours after administration of the study drug. Starting from Cycle 4, the ECG will be obtained at every treatment cycle within 1 hour following study drug administration and at EOT/early withdrawal visit (time window: ± 5 min).

⁷ Tumor assessments should be performed at baseline, and every 3 cycles prior to next cycle until progression of disease. For patients who meet DC criteria after the first 3 cycles of study treatment, additional radiological tumor assessments should be performed at Week 12. Any additional assessment can be arranged when clinically indicated.

⁸ Test results within 7 days prior to Cycle 1, Day 1 (C1D1) are acceptable. Only items not performed or obtained within 7 days prior to C1D1 should be tested.

⁹ Serum pregnancy test for women of childbearing potential must be performed ≤ 14 day prior to first dose.

¹⁰ Quality of Life questionnaires (EORTC QLQ-C30 and H&N35) should be performed at Screening and all clinic visits (before study drug administered, where applicable, except at C1D1).

¹¹ Blood Sample for VEGF and CEC will be taken immediately pre-infusion then at 6, 10 and 24 hours after start of infusion on C1D1 and C3D15. Blood Samples for CEP will be taken immediately pre-infusion and C3D15.

¹² Tumor microvessel density and blood flow by DCE-MRI at both baseline (-28 to -1 Day) and 6 hours (+/- 1hour) after the infusion of the drug on C1D1.

¹³ Follow-up for survival status will be performed via telephone call if the site is unable to confirm via chart review or clinical visit.

¹⁴ Cancer therapies evaluated at the Follow-Up visit or phone call include anti-cancer medications, cancer-related radiotherapy and cancer-related surgery/procedures since last contact.

¹⁵ To be performed when necessary at the patient's request or per Investigator decision.

¹⁶ To be performed for all patients at baseline and then during the trial only if grade 2 or above neurological symptoms experienced by the patient after receiving treatment with SCB01A. Refer section 5.9 for further details.

1. Introduction

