1. Known primary CNS malignancy or CNS involvement (except for brain metastases that have been treated and are stable and patient is off steroids);
2. Systemic cancer therapy, Chemotherapy, radiation therapy, major surgery or investigational agents less than 4 weeks prior to study drug treatment;
3. History of malignancy other than head and neck cancer. Second primary head and neck tumors are excluded with the exception of early stage non-melanoma skin cancer or carcinoma *in situ* of cervix;
4. Ultrasound or radiological evidence of liver cirrhosis;
5. Severe pulmonary obstructive or restrictive disease;
6. Uncontrolled inflammatory disease (autoimmune or infectious);
7. Clinically significant cardiac disease (NYHA class > 2);
8. Other serious illness or medial conditions, such as active infection, unresolved bowel obstruction, or psychiatric disorders;
9. Known HIV positivity;
10. Participation in another clinical trial or treatment with any investigational drug within 30 days prior to study entry;
11. QTc $> 450 \text{ msec}$;
12. Pregnant or breast-feeding patients, and men and women of child-bearing potential not using effective contraception while on study treatment; Known hypersensitivity to any component of SCB01A;

	
13. History of exposure to SCB01A or its analogues;
 
14. History of active or significant neurological disorder or psychiatric disorder that would prohibit the understanding and giving of informed consent, or would interfere with the clinical and radiological evaluation of central nervous system during the trial;
 
15. Any other reason the investigator deems the patient to be unsuitable for the study

Duration of Treatment:	Patients will receive the recommended dose of monotherapy of SCB01A for 9 weeks (3wk*3 cycles) or until disease progression, intolerable toxicity, consent withdrawal or death, whichever occurs first.

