1.1. Background

Vascular disrupting agents (VDAs) are designed to disrupt the already abnormal vasculature that supports tumors by targeting their already dysmorphic endothelial cells. VDAs induce rapid and selective shutdown of the tumor blood supply resulting in tumor death while leaving the blood supply in normal tissues relatively intact^{3,4}. The largest group of VDAs is the tubulin-binding combretastatins. Combretastatin A4 phosphate (CA4P) is a small organic molecule found in the bark of the African bush willow tree (*Combretum caffrum*)³. Endothelial cells have been shown to be particularly sensitive to the effects of CA4P compared with various other cell types and several preclinical studies have demonstrated selective *in vitro* activity of CA4P against proliferating endothelial cells³.

SCB01A is a novel heterocyclic combretastatin A-4 (CA-4) analogue that binds to the colchicines-binding site of the β-subunit of tubulin thereby inhibiting polymerization and effectively preventing mitosis in a manner similar to that seen with other “spindle poisons”, e.g., vincristine, vinblastine and vinorelbine, which are in use as cancer chemotherapeutic agents. Because SCB01A has VDAs property, SynCore plans to develop SCB01A as a treatment for a variety of oncologic indications such as non-small cell lung cancer, breast cancer, head and neck cancer, acute lymphoblastic leukemia, nephroblastoma and testicular cancer.

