3.4. End of Treatment (EOT) Evaluation/Early Withdrawal

EOT visit should be conducted 21 ± 2 days after the last infusion. Early withdrawal visit should be conducted within 21 days after the patient receives the last dose of study treatment.

The following assessments will be performed at the EOT/early withdrawal visit:

- Physical examination
- Vital signs
- ECOG performance status
- AEs
- Concomitant medication
- 12-lead ECG
- Tumor assessment (radiological imaging)
- Urinalysis
- Laboratory tests (hematology, clinical chemistry and coagulation)
- EORTC QLQ-C30 and H&N35

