3.8. Selection of Study Population

3.8.1. Inclusion Criteria:

1. Aged \geq 20 years;
2. Signed informed consent obtained prior to initiation of any study-specific procedures and treatment;
3. Histological or cytological confirmed squamous cell carcinoma of head and neck;
4. Patients with non-resectable, unfeasible radiotherapy, recurrent or metastatic head and neck squamous cell carcinoma, after previous treatment with platinum agent;
5. At least one measurable tumor lesion as defined by RECIST version 1.1 as assessed by the investigator (local radiological image assessment);
6. Eastern Cooperative Oncology Group (ECOG) Performance Status (PS) 0-2;
7. Life expectancy of 12 weeks or longer;
8. Patients must have radiological measurable or clinically evaluable disease. Physical examination and radiographic studies have to be performed within 28 days of enrolment;
9. Concurrent local therapy is not allowed, but concurrent palliative radiation

therapy to non-measurable sites of disease such as painful bone metastasis is permitted;

10. All eligible patients of childbearing potential have to use effective contraception; that is, double barrier contraceptive methods;
11. Documented progressive disease within past 6 months;
12. Adequate bone marrow reserve, cardiac, renal and liver function:
 - a. Absolute neutrophil count (ANC) $> 1.5 \times 10^9/L$;
 - b. White blood cell (WBC) $> 3 \times 10^9/L$
 - c. Platelet count $> 75 \times 10^9/L$;
 - d. Hemoglobin $> 9 \text{ g/dL} (> 5.6 \text{ mmol/l})$;
 - e. Prothrombin time (PT)/international normalized ratio (INR) $\leq 1.5 \times$ upper limit of normal (ULN)
 - f. Creatinine clearance (Cockcroft & Gault formula) $> 50 \text{ mL/min}$;
 - g. Alanine aminotransferase (ALT, SGPT) and aspartate aminotransferase (AST, SGOT) and Alkaline Phosphatase (ALP) $< 3 \times \text{ULN}$.
 - h. Serum albumin $\geq 3 \text{ g/dL}$;
 - i. INR $\leq 1.5 \times \text{ULN}$
 - j. Total Bilirubin $\leq 1.5 \times \text{ULN}$

3.8.2. Exclusion Criteria:

1. Known primary CNS malignancy or CNS involvement (except for brain metastases that have been treated and are stable and patient is off steroids);
2. Chemotherapy, radiation therapy, major surgery or investigational agents less than 4 weeks prior to study drug treatment;
3. History of malignancy other than head and neck cancer. Second primary head and neck tumors are excluded with the exception of early stage non-melanoma skin cancer or carcinoma *in situ* of cervix;

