7.2. Adverse Event Reporting

All AEs occurring during the study (from the time of informed consent obtained until 28 days after the last dose of study treatment) observed by the Investigator or reported by the patient (whether or not attributed to study drug), will be reported on the eCRF. Clinically significant AEs considered related or non-related to the IP by the Investigator or the Sponsor will be followed until resolved or considered stable by the Investigator. The following information must be provided: description; dates of onset and resolution; severity; assessment of relatedness to IP, other suspect drug, or device; and action taken. The investigator may be asked to provide follow-up information.

All AEs, serious or not, that result in the patient's permanent withdrawal of IP or from the study will be discussed between the investigator and medical monitor. The eCRF for EOT/Early Withdrawal Visit should be completed including reason of withdrawal.

It will be the investigator's clinical judgment whether or not an AE is of sufficient severity to require the patient's removal from study treatment. A patient may also voluntarily withdraw from study treatment due to what he or she perceives as an intolerable AE. If either of these occurs, the patient must undergo EOT assessment and be given appropriate care under medical supervision until symptoms cease or the condition becomes stable.

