7.5. Pregnancies

All initial reports of pregnancy must be reported to the Sponsor within 24 hours of the Investigator knowledge of the event using the appropriate pregnancy form.

For IP, an exposure during pregnancy occurs if:

- A female becomes, or is found to be, pregnant either while receiving or having been directly exposed (e.g., environmental exposure) to the IP, or the female becomes, or is found to be, pregnant after discontinuing and/or being directly exposed to the IP (maternal exposure) for 28 days after last dose of or exposure to IP.
- A male partner of a pregnant female has been exposed to the IP, either due to treatment or environmental exposure, within 3 months prior to the time of conception and/or is exposed during his partner's pregnancy (paternal exposure).

If any study patient or study patient's partner becomes or is found to be pregnant during the study patient's treatment with the IP or exposure as defined above, the Investigator must submit this information on a Pregnancy form to the Sponsor (or its designated representative). In addition, the Investigator must submit information regarding environmental exposure to an IP in a pregnant woman (e.g., a patient reports that she is pregnant and has been exposed to a cytotoxic product by inhalation or spillage) using the Pregnancy form. This must be done irrespective of whether an AE has occurred and within 24 hours of awareness of the pregnancy. The information submitted should include the anticipated date of delivery (see following information related to induced termination of pregnancy).

Follow-up is conducted to obtain pregnancy outcome information on all exposure during pregnancy reports with an unknown outcome. The Investigator will follow the pregnancy until completion or until pregnancy termination (e.g., induced abortion) and then notify the Sponsor or its designated representative of the outcome as a follow-up to the initial Pregnancy form. In the case of a live birth, the structural integrity of the neonate can be assessed at the time of birth. In the event of a termination, the reason(s) for termination should be specified and, if clinically possible, the structural integrity of the terminated fetus should be assessed by gross visual inspection (unless pre-procedure test findings are conclusive for a congenital anomaly and the findings are reported).

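### Contraception is required only during study treatment, although the protocol counts pregnancies as exposed for 28 days (women) and 3 months (men) after dosing

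*Protocol*

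**What the plan says.** Contraception appears in two eligibility criteria, each printed in the synopsis and again in Section 3.8.

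- Inclusion criterion 10 (synopsis; Section 3.8.1): "All eligible patients of childbearing potential have to use effective contraception; that is, double barrier contraceptive methods". It gives a method and no duration.
- Exclusion criterion 12 (synopsis; Section 3.8.2) excludes "men and women of child-bearing potential not using effective contraception while on study treatment". This is the only duration stated, and the criterion does not say when treatment ends.

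Section 7.5 defines which pregnancies count as exposed. For women the period is "maternal exposure) for 28 days after last dose of or exposure to IP". For men it covers exposure "within 3 months prior to the time of conception", as well as exposure during the partner's pregnancy.

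Two other sections bear on when treatment could be taken to end and where the 28 days comes from. Section 3.4 sets the closing visits: "EOT visit should be conducted 21 ± 2 days after the last infusion", and "Early withdrawal visit should be conducted within 21 days after the patient receives the last dose of study treatment". Section 7.2 collects adverse events "until 28 days after the last dose of study treatment".

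**The concern.** The contraception requirement and the pregnancy exposure definition do not cover the same time. The protocol asks sites to report and follow pregnancies over a period that extends beyond the last dose, but no supplied text asks patients to keep avoiding conception through that period.

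The mechanism makes this more than tidiness. Section 1.1 describes SCB01A as binding tubulin, "thereby inhibiting polymerization and effectively preventing mitosis in a manner similar to that seen with other" spindle poisons already used as chemotherapy, so harm to a fetus is a plausible hazard.

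Nothing later in the schedule compensates. The serum pregnancy test is required only within 14 days before the first dose (Section 5.5; Tables 1 and 2). No pregnancy test is listed at the end-of-treatment visit (Section 3.4). Follow-up may be by telephone and is directed at survival and subsequent therapy (Section 3.5).

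**Working it through.** The plan states no figure to reproduce. The check is how many days of each Section 7.5 period remain once the contraception requirement has lapsed.

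**Inputs**
- Women: 28 days after the last dose (Section 7.5).
- Men: 3 months between exposure and conception (Section 7.5), taken as 90 to 92 days and counted from the last infusion. Both are assumptions.
- Dosing on Days 1 and 8 of a 21-day cycle (Section 3.1). After a Day 8 dose the cycle has 21 − 8 = 13 days left.
- End-of-treatment visit: 21 ± 2 days, i.e. 19 to 23 days after the last infusion (Section 3.4).
- Early withdrawal visit: 0 to 21 days after the last dose (Section 3.4).

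**Formula**

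Uncovered days = Section 7.5 period − days from last dose to the assumed end of treatment.

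The smallest value pairs the shortest period with the latest end; the largest pairs the longest period with the earliest end.

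| Treatment taken to end at | Days after last dose | Women uncovered | Men uncovered |
|---|---|---|---|
| Last infusion | 0 | 28 − 0 = 28 | 90 − 0 to 92 − 0 = 90 to 92 |
| End of cycle after a Day 8 dose | 13 | 28 − 13 = 15 | 90 − 13 to 92 − 13 = 77 to 79 |
| End-of-treatment visit | 19 to 23 | 28 − 23 to 28 − 19 = 5 to 9 | 90 − 23 to 92 − 19 = 67 to 73 |
| Early withdrawal visit | 0 to 21 | 28 − 21 to 28 − 0 = 7 to 28 | 90 − 21 to 92 − 0 = 69 to 92 |

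The overall range is 5 to 28 days for women and 67 to 92 days for men, and it is above zero on each of these readings. Even the smallest male figure exceeds nine weeks (67 / 7 = 9.6).

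**Can the exclusion wording be stretched to cover follow-up?** Not comfortably. Section 3.9.2 distinguishes stopping study treatment from leaving the study, and Section 3.5 places follow-up after treatment has been discontinued.

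**The case against.** The case on the other side has real content.

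- **Unseen documents.** The consent pages were removed, and the Investigator's Brochure is not supplied. Either may tell patients to continue contraception for longer. This stands as a limit: the point concerns what the protocol states, and it is not shown that patients went without an instruction. If the consent text does set a longer period, the criteria that sites apply would still need to match it.
- **Section 7.5 is a reporting rule.** It says which pregnancies must be notified, and a reporting period may reasonably be wider than a restriction on patients. The 28 days equals the general adverse event period in Section 7.2 and could simply have been carried over. The maternal definition also captures pregnancies found after treatment but conceived during it. So there is no contradiction between the sections, and the evidence for women is weaker. The male period answers this better: it does not match the adverse event period and is tied to conception.
- **The right duration cannot be derived.** Section 1.1 says that genotoxicity and pharmacokinetics were studied, but no genotoxicity result or half-life is supplied. This stands. The Section 7.5 periods are a minimum for internal consistency and are not shown to be sufficient.
- **Inclusion criterion 10 is open-ended.** It could be read as lasting throughout participation, a reading the table does not include. That leaves the obligation unclear, because the only duration actually stated ends with treatment.
- **Practical weight.** The number of fertile patients is unknown, the disease is advanced, and the study ended in the run-in phase with five patients enrolled (SAP Section 1). An amendment now would help only if the protocol or its criteria are reused. That lowers urgency but does not make the stated duration adequate for a trial planned for up to 64 patients.

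**Conclusion.** The concern holds. The stated duration lets contraception stop while a conception would still count as exposed under Section 7.5, most clearly for men. The days in question measure time at risk under the protocol's own definition; they do not estimate how many pregnancies would occur.

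The conclusion rests on three things: 3 months taken as 90 to 92 days from the last infusion, the four readings of when treatment ends, and the protocol text alone. Confidence is medium, mainly because the consent text was not seen. This is an omission that should be corrected for patient and partner safety.

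**What to change.** Amend inclusion criterion 10 and exclusion criterion 12, in the synopsis and in Sections 3.8.1 and 3.8.2, to require effective contraception during treatment and, after the last dose, for at least 28 days in women and at least 3 months in men. The sponsor's medical team should lengthen these periods if the toxicology or pharmacokinetic data call for it. Check that the consent text gives the same periods and align it if not. As recruitment has ended, the steps that remain useful are to confirm what the five enrolled patients were told and to carry the corrected wording into any later SCB01A protocol.

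The cost is a few words in two criteria, plus the consent text if it differs. No visits or tests are added. The downside is a modestly longer contraception obligation for patients.
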